2. LIST OF ABBREVIATIONS

See Medicine Glossary:

<http://glossary>

Term	Definition / description
ADS	Analysis data set
ALT	Alanine transaminase
AST	Aspartate transaminase
AUC _{0-∞}	Area under the concentration-time curve of the analyte in plasma over the time interval from 0 extrapolated to infinity
AUC _{0-tz}	Area under the concentration-time curve of the analyte in plasma over the time interval from 0 to the last quantifiable data point
AUC _{τ,ss}	Area under the concentration-time curve of the analyte in plasma at steady state over a uniform dosing interval τ
BMI	Body mass index
CARE	Clinical data Analysis and Reporting Environment
CI	Confidence interval
C _{max}	Maximum measured concentration of the analyte in plasma
C _{max,ss}	Maximum measured concentration of the analyte in plasma at steady state over a uniform dosing interval τ
C _{min,ss}	Minimum concentration of the analyte in plasma at steady state over a uniform dosing interval
CV	Arithmetic coefficient of variation
ECGPCS	ECG Pharmacokinetic Concentration Set
EDMS	Electronic documentation management system
EOT	End of Trial
gCV	Geometric coefficient of variation
gMean	Geometric mean
λ_z	Terminal rate constant of the analyte in plasma
Max	Maximum
MedDRA	Medical Dictionary for Regulatory Activities
Min	Minimum
N	Number of non-missing observations
Nobs	Number of observations
P10	10th percentile

Term	Definition / description
P90	90th percentile
PKS	Pharmacokinetic parameter analysis set
PT	Preferred term
Q1	1st quartile
Q3	3rd quartile
R _{A,AUC}	Accumulation ratio based on AUC _{0-τ}
R _{A,Cmax}	Accumulation ratio based on C _{max,ss}
RAGe	Report Appendix Generator system
REP	Residual effect period
RPM	Report planning meeting
SCR	Screening
SD	Standard deviation
SOC	System organ class
SRD	Single rising dose
t _{max}	time from dosing to maximum measured concentration of the analyte in plasma
TMF	Trial master file
TS	Treated set
ULN	Upper limit of normal
WHO-DD	World Health Organization Drug Dictionary

3. INTRODUCTION

As per ICH E9 (1) the purpose of this document is to provide a more technical and detailed elaboration of the principal features of the analysis described in the protocol, and to include detailed procedures for executing the statistical analysis of the primary and secondary variables and other data.

This Trial statistical analysis plan (TSAP) assumes familiarity with the Clinical Trial Protocol (CTP), including Protocol Amendments. In particular, the TSAP is based on the planned analysis specification as written in CTP Section 7 “Statistical Methods and Determination of Sample Size”. Therefore, TSAP readers may consult the CTP for more background information on the study, e.g., on study objectives, study design and population, treatments, definition of measurements and variables, planning of sample size, randomisation.

Study data (including data entered in the RAVE EDC system and external data provided by suppliers) will be stored in a Clinical Data Repository (CDR).

Pharmacokinetic (PK) parameters will be calculated using Phoenix WinNonlin™ software (version 8.1 or higher, [REDACTED])

The statistical analyses will be performed within the validated working environment CARE, including SAS™ (current Version 9.4, by [REDACTED]), and a number of SAS™-based tools (e.g., macros for the analyses of AE data or laboratory data; Report Appendix Generator system (RAGe) for compilation/formatting of the CTR appendices).

4. CHANGES IN THE PLANNED ANALYSIS OF THE STUDY

All analyses as planned in the CTP will be performed and are described in more detail in this TSAP. The following changes compared to the protocol will be made:

Initiation of trial part II will be delayed and it is uncertain, if Part II will be done at all. Due to this, analysis of Part I will already be conducted and finalized directly after completion of Part I. If Part II will not be conducted, the TSAP will be amended accordingly.

By the date of this revision (TSAP version 2.0), it is known that Part II of the study will not be conducted due to termination of the development of the BI 706321 program in Crohn's Disease. It is important to note that this decision is not based on any safety finding for BI 706321. Therefore, descriptions regarding analyses for Part II of the study have been removed from all sections of the TSAP.

Linearity analysis will be adapted in line with updated BI standards. Originally, the linearity index model included a random effect for subject. This random effect will be excluded from the model as subject is already taken into account with the random error e_{ij} associated with subject j at AUC type i .

Pre-dose plasma concentrations $C_{pre,ss}$, $C_{pre,N}$ and $C_{avg,ss}$ which were defined in the CTP as further endpoints, will not be analysed as further endpoints. They will be analysed as part of the analysis of plasma concentration time data, and will be identified by their planned sampling time, e.g. concentration at planned time 431:45 h ($= C_{pre,ss}$), 120 h ($= C_{pre,1}$), 168 h ($C_{pre,3}$), 192 h ($C_{pre,4}$) etc. (Please refer the below table as reference). Instead of $C_{avg,ss}$, $C_{avg,14}$ will be calculated. However, this is not a deviation from the statistical methods described in the revised CTP.

Table 4: 1 Definition of trough concentrations data

Day	6	8	9	10	11	12	13
PTM	120:00	168:00	192:00	216:00	240:00	264:00	288:00
PK param	$C_{pre,1}$	$C_{pre,3}$	$C_{pre,4}$	$C_{pre,5}$	$C_{pre,6}$	$C_{pre,7}$	$C_{pre,8}$

Day	14	15	16	17	18	19	20
PTM	312:00	336:00	360:00	384:00	408:00	431:45	456:00
PK param	$C_{pre,9}$	$C_{pre,10}$	$C_{pre,11}$	$C_{pre,12}$	$C_{pre,13}$	$C_{pre,14}$ ($C_{pre,ss}$)	$C_{\tau,14}$

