3. N=5

4. AUC_{0-tz} value is given since AUC_{0-∞} is not evaluable

--- not available

The PK of BI 706321 was also evaluated after once daily administration over a period of 14 days. Preliminary PK parameters of BI 706321 derived based on planned time in trial 1425-0002 are summarized in [Table 1.2.1: 2](#). The geometric mean concentration-time profiles are shown in [Figure 1.2.1: 1](#) below. The steady state geometric mean plasma exposure (AUC of 574 nmol·h/L and C_{max} of 39.9 nmol/L) with 10 mg BI 706321 QD was below the maximum allowable BI 706321 exposure predefined in trial 1425-0002 based on NOAEL in the 4-week cynomolgus monkey study (AUC₀₋₂₄ of 693 nmol·h/L and C_{max} of 86.1 nmol/L), although the exposures of 3 subjects were slightly higher than the predefined exposure limit

Proprietary confidential information © 2021 Boehringer Ingelheim International GmbH or one or more of its affiliated companies

Table 1.2.1: 2

Preliminary PK parameters^{P1P} of BI 706321 after single and multiple oral administration of BI 706321 over 14 days in the study 1425-0002¹

	2 mg (N=8)	5 mg (N=8)	8 mg (N=8)	10 mg (N=8)
t _{max} ² (h)	5.00 (2.00-6.00)	5.00 (2.00-6.00)	5.50 (3.00-6.00)	5.00 (4.00-5.00)
t _{max,ss} ² (h)	5.00 (3.00-5.00)	5.00 (4.00-5.00)	4.00 (1.00-5.00)	5.00 (1.00-6.00) ⁴
AUC ₀₋₂₄ ³ (nmol*h/L)	38.3 (48.1)	85.1 (31.0)	140 (42.6)	155 (30.0)
AUC _{t,ss} ³ (nmol*h/L)	88.1 (34.5)	234 (34.8)	517 (29.9)	574 (35.6) ⁴
C _{max} ³ (nmol/L)	2.85 (53.8)	6.47 (29.1)	10.6 (38.6)	11.5 (33.6)
C _{max,ss} ³ (nmol/L)	5.69 (41.8)	14.7 (43.1)	34.7 (38.5)	39.9 (35.7) ⁴
C ₂₄ ³ (nmol/L)	1.27 (38.8)	2.43 (34.4)	3.78 (43.6)	4.68 (26.3)
C _{24,ss} ³ (nmol/L)	3.12 (39.9)	7.93 (32.3)	16.4 (22.4)	18.6 (38.0) ⁴
t _{1/2} ³ (h)	40.8 (37.7)	41.7 (19.4)	36.3 (21.4)	43.2 (20.4)
t _{1/2,ss} ³ (h)	74.4 (49.5)	70.4 (34.8)	46.8 (21.7)	76.5 (32.2) ⁴
RA _{Cmax} ³	2.00 (27.7)	2.28 (23.1)	3.29 (24.5)	3.34 (15.2) ⁴
RA _{AUCt} ³	2.30 (33.2)	2.75 (20.8)	3.69 (23.9)	3.58 (19.8) ⁴

1. Derived based on planned time

2. Median (range)

3. Geometric mean (gCV%)

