3. DESCRIPTION OF DESIGN AND TRIAL POPULATION

3.1 OVERALL TRIAL DESIGN AND PLAN

Part I:

This multiple-rising dose trial is designed as double-blind, randomised, and placebo-controlled within parallel dose groups.

It is planned to include a total of 48 healthy Japanese male subjects in the trial. The subjects will be assigned to 4 groups consisting of 12 subjects per group; the groups will be dosed sequentially (see Table 3.1: 1). Within each dose group, 9 subjects will receive BI 706321 and 3 will receive placebo. Only one dose is tested within each dose group.

The trial schedule and design are depicted in Figure 3.1: 1 below.

[figure not shown]

Figure 3.1: 1

Trial design "Part I"

The dose groups to be evaluated are outlined in Table 3.1: 1 below.

Table 3.1: 1 Dose groups

Dose Group	1	2	3	4
Daily dose (mg)	2	5	8	10
Number of subjects	12	12	12	12
Subjects receiving placebo	3	3	3	3
Subjects receiving BI 706321	9	9	9	9

The groups will be dosed consecutively in ascending order, and a time interval of at least 7 days will be maintained between the last drug administration to subjects in the previous dose group and the first drug administration to subjects in the subsequent dose group. The decision to treat the next dose group will be based upon safety and tolerability data of all the preceding dose groups. The next dose group will only be treated if, in the opinion of the investigator, no safety concerns have arisen in the preceding dose groups (i.e. no dose-limiting events occurred), and if none of the pre-specified trial-specific stopping criteria have been met (refer to Section 3.3.4.3).

Proprietary confidential information © 2021 Boehringer Ingelheim International GmbH or one or more of its affiliated companies

A documented safety review must take place prior to each dose escalation. Furthermore, an unscheduled safety review meeting can be requested anytime by the Principal Investigator (or an authorised deputy) or the sponsor of the study (for instance, due to the occurrence of any unforeseen adverse events).

Although no formal Safety Review meeting will take place within a given dose group, safety will be continuously monitored during this trial, and an individual will only be dosed in the absence of any safety concern (i.e. no dose-limiting events occurred) and if none of the pre-specified trial-specific stopping criteria have been met (refer to Section [3.3.4.3](#)).

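### Does removing the random subject effect from the linearity model mean that a subject's AUC values are analysed as independent?

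*SAP*

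**What the plan says.** SAP section 4 (Changes in the planned analysis of the study) records one change to the linearity analysis, made to follow updated company standards. It states the starting point, "Originally, the linearity index model included a random effect for subject", then the change and its reason: "This random effect will be excluded from the model as subject is already taken into account with the random error" e_ij, which is "associated with subject j at AUC type i".

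This is a short change note. It does not give the model equation, the AUC types compared, the covariance of the errors or the confidence level. Those details belong to sections that cannot be read in the public files. The SAP table of contents shows a redacted entry between 7.5.2 and 7.7, and the SAP text makes the same jump. The protocol text goes from 7.3.2 to 7.3.4.

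Protocol 7.2 plans no hypothesis test and treats confidence intervals as exploratory estimates. On group size, Protocol 3.1 says: "Within each dose group, 9 subjects will receive BI 706321 and 3 will receive placebo".

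**The concern.** A linearity index compares AUC values from the same subject after the first dose and at steady state. In a mixed model the random subject effect usually carries the correlation between those values. If it is removed and the residuals are ordinary independent errors, the comparison becomes one of two separate samples. Between-subject variance then enters the standard error of a within-subject ratio. Read that way, the stated reason is wrong, since an error with a subject index is not thereby correlated within subject.

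The interval for the index would then be much too wide, and real time-dependence in the kinetics could pass as linear. The earlier multiple-dose trial gives some reason to look: in Protocol Table 1.2.1: 2 the AUC accumulation ratio is 2.30 at 2 mg, 2.75 at 5 mg, 3.69 at 8 mg and 3.58 at 10 mg.

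**Working it through.** The plan states no interval width or correlation for the linearity index, so there is no figure of its own to reproduce. Two questions can be checked: what independence would cost, and whether the plan implies independence.

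**Inputs.** Geometric CVs come from Protocol Table 1.2.1: 2 (trial 1425-0002, preliminary, planned times), with n = 9 active subjects per dose from Protocol 3.1. AUC0-24 stands in for the first-dose AUC. Two AUC types, a separate analysis per dose and a 90% level are assumptions.

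**Input check.** AUCτ,ss divided by AUC0-24 (geometric means) should match the tabulated ratio:
- 2 mg: 88.1/38.3 = 2.30
- 5 mg: 234/85.1 = 2.75
- 8 mg: 517/140 = 3.69
- 10 mg: 574/155 = 3.70, against 3.58 in the table, where steady-state N is 7 and not 8

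**Formulas.** With v1, v2 and vR the log-scale variances of first-dose AUC, steady-state AUC and their within-subject ratio:
- v = ln(1 + gCV²)
- cov = (v1 + v2 − vR)/2 and ρ = cov/√(v1·v2)
- SE inflation under independence = √((v1 + v2)/vR)
- 90% interval factor: paired exp(1.860·√(vR/9)), independent exp(1.746·√((v1 + v2)/9)), using t with 8 and 16 degrees of freedom

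| Dose | gCV% (first dose, steady state, ratio) | v1 | v2 | vR | ρ | SE inflation | Paired factor | Independent factor | Log-width ratio |
|---|---|---|---|---|---|---|---|---|---|
| 2 mg | 48.1, 34.5, 33.2 | 0.2081 | 0.1125 | 0.1046 | 0.71 | 1.75 | 1.22 | 1.39 | 1.64 |
| 5 mg | 31.0, 34.8, 20.8 | 0.0918 | 0.1143 | 0.0424 | 0.80 | 2.21 | 1.14 | 1.30 | 2.07 |
| 8 mg | 42.6, 29.9, 23.9 | 0.1668 | 0.0856 | 0.0555 | 0.82 | 2.13 | 1.16 | 1.34 | 2.00 |
| 10 mg | 30.0, 35.6, 19.8 | 0.0862 | 0.1193 | 0.0385 | 0.82 | 2.31 | 1.13 | 1.30 | 2.17 |

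So **if** the errors were independent within subject, a nominal 90% interval would be about twice as wide as it should be. By simulation it would cover 99% or more of the time.

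**If the errors are correlated within subject.** Give (e_1j, e_2j) an unstructured covariance and leave out the random effect. The variance of the within-subject difference is v1 + v2 − 2·cov. At 10 mg, cov = (0.0862 + 0.1193 − 0.0385)/2 = 0.0835, so the variance is 0.2055 − 0.1670 = 0.0385. That is vR, the paired variance, and the interval does not widen.

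Two values per subject have three second moments: two variances and one covariance. The unstructured residual uses all three. A subject variance on top would be a fourth parameter for three quantities and could not be estimated separately. With more AUC types the same holds, because a random intercept only adds a constant to every element of a matrix that is already free. In such a model, removing the random effect is the correct simplification, and the reason in SAP section 4 is accurate.

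**Which case applies.** The note calls e_ij a random error that already takes subject into account. That is true of a residual vector grouped by subject and false of independent residuals. No sentence in either document says the errors are independent. Where SAP mixed models can be read (10.1.2 and 10.1.4), a covariance blocked by subject is written out in the code. This does not prove what the linearity code does, but it gives no support to the independent reading.

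**The case for a change.** The strongest opposing argument is that the sentence itself is visible and gives the sponsor's own reason for a change. Taken literally, an index on an error term says nothing about correlation, so the reason is incomplete without a covariance. There is also a point about incomplete pairs. Under SAP 6.3 a subject stays in the pharmacokinetic set with a single parameter value, and an independence model would then move the estimate towards the unpaired ratio, as 3.70 against 3.58 at 10 mg illustrates.

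Part of this stands. The note is terse, and a reader of the public files cannot confirm the covariance of e_ij. The arithmetic is also sound as a conditional statement. But a terse change note is not a wrong model, and a covariance that would be stated in a redacted section cannot be counted as absent. The point about incomplete pairs needs the same unproven independence. What remains is a wish to see the model in full, which does not show a fault in the analysis.

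The stakes are also limited. With complete pairs the point estimate is the same under either structure. The within-subject accumulation ratio for AUC is itself a secondary endpoint (SAP 5.2.2), summarised with geometric mean, geometric CV and percentiles (SAP 7 and 7.5.2). The paired information is therefore reported whatever the linearity model does. That ratio compares AUCτ,ss with AUC0-24, so values above 1 are expected with once-daily dosing and first-dose half-lives of 36.3 to 43.2 h. Only its change with dose could hint at non-linearity, and it does not rise further from 8 to 10 mg.

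**Conclusion.** The concern does not hold. The widening of 1.64 to 2.17 times is correct only if a subject's errors are independent, and neither document says so. With a within-subject covariance for e_ij, the other reading of the note and the one under which its reason is true, the random subject effect is redundant and the widening is nil.

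The conditional figure rests on further assumptions: AUC0-24 in place of the first-dose AUC actually used, preliminary data from another trial, two AUC types, a separate analysis of 9 subjects per dose, and a 90% level. The conclusion that no fault is shown rests on none of these. It rests on the absence of any statement of independence and on the redaction of the sections where the covariance would be given.

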5. ENDPOINTS

5.1 PRIMARY ENDPOINT

Section 2.1.2 of the CTP:

The primary endpoint for assessment of safety and tolerability of BI 706321 is the percentage of subjects with drug-related adverse events.

5.2 SECONDARY ENDPOINTS

5.2.1 Key secondary endpoint

This section is not applicable as no key secondary endpoints have been defined in the CTP.

5.2.2 Secondary endpoints

Pharmacokinetic endpoints for BI 706321 are defined as secondary endpoints of the trial.

Section 2.1.3 of the CTP:

The following pharmacokinetic parameters will be determined if feasible:

Part I

Single dose part (after the first dose):

- $AUC_{0-\infty}$ (area under the concentration-time curve of the analyte in plasma over the time interval from 0 extrapolated to infinity)
- C_{max} (maximum measured concentration of the analyte in plasma)
- t_{max} (time from dosing to maximum measured concentration of the analyte in plasma)

After the last dose:

- $AUC_{\tau,ss}$ (area under the concentration-time curve of the analyte in plasma at steady state over a uniform dosing interval τ)
- $C_{max,ss}$ (maximum measured concentration of the analyte in plasma at steady state over a uniform dosing interval τ)
- $C_{min,ss}$ (minimum concentration of the analyte in plasma at steady state over a uniform dosing interval τ)
- $R_{A,Cmax}$ (accumulation ratio based on $C_{max,ss}$)
- $R_{A,AUC}$ (accumulation ratio based on $AUC_{0-\tau}$)

Safety and tolerability endpoints

[figure not shown]
Section 2.2.2.1 of the CTP:

Safety and tolerability of BI 706321 will be assessed based on:

- *AEs (including clinically relevant findings from the physical examination)*
- *Safety laboratory tests*
- *12-lead ECG*
- *Vital signs (blood pressure, pulse rate, body temperature)*

12-lead ECG endpoints:

For the definition of baseline and a summary of time points scheduled for ECG recording and central evaluation please refer to [Section 6.7](#).

6. GENERAL ANALYSIS DEFINITIONS

6.1 TREATMENTS

For basic study information on treatments to be administered, assignment of treatment groups and selection of doses, please see CTP, Sections 3 and 4.

In Part I, a double-blind, randomised and placebo-controlled parallel-group trial in Japan is planned.

A total of 48 Japanese healthy male subjects will be treated with single and multiple doses of BI 706321. The subjects will be assigned to 4 dose groups of 12 subjects. In each dose group, 9 subjects will be randomised to active treatment and 3 subjects will be randomised to placebo. All subjects will receive a single dose on Day 1 (single dose evaluation), and further 2 weeks with daily doses of study treatment starting on Day 6 (multiple dose evaluation). For details of dosage and formulation see [Table 6.1: 1](#).

Table 6.1: 1 Treatments and labels used in the analysis – Part I

Treatment		Short label
P*	Placebo	Placebo – Japanese
A	BI 706321, 2 mg TABLET, FILM COATED QD ORAL	BI 2mg – Japanese
B	BI 706321, 5 mg TABLET, FILM COATED QD ORAL	BI 5mg – Japanese
C	BI 706321, 8 mg TABLET, FILM COATED QD ORAL	BI 8mg – Japanese
D	BI 706321, 10 mg TABLET, FILM COATED QD ORAL	BI 10mg – Japanese

* For data analysis purposes, the placebo control group of Part I (Japan) will include all subjects of all dose groups in Part I treated with placebo.

Section 1.2.2 of the CTP:

*The Residual Effect Period (REP) of BI 706321 is 16 days and is projected based on 5*terminal t_{1/2} from preliminary PK data of Trial 1425-0002. This is the period after the last dose with measurable drug levels and/or pharmacodynamic effects still likely to be present.*

The following study phases will be defined for the analysis of adverse events (AEs):

- **Screening** (ranging from 0:00 h on day of informed consent until first administration of study medication (BI/Placebo))
- **On treatment** (ranging from the first time of administration of BI or Placebo until 16 days (384 hours) after the last time of administration of BI/Placebo)
- **Follow-up (F/U)** (ranging from 16 days (384 hours) after last administration of BI or Placebo until 0:00 h on day after trial termination date)

In Part I, the end-of-trial visit is planned to take place on day 27, whereas last drug administration is planned on day 19. Consequently, follow-up phase does not apply to Part I.

Section 7.3.4 of the CTP: *Note that AEs occurring after the last per protocol contact but entered before database lock will be reported to Pharmacovigilance only and will not be captured in the trial database.*

Displays of AEs will be stratified by treatment group as specified in [Table 6.1: 1](#). The results will be presented separately for each trial part if not stated otherwise. The following AE displays will be provided in the report:

In Section 15.3 and Appendix 16.1.13.1.8 (for ClinicalTrials.gov) of the CTR displays, the on treatment phase will be analysed (labelled with the name of the study treatment (short label)). Screening and follow-up phases will not be included in this analysis.

The following totals will be provided for Section 15.3 (except for ECG analysis):

- a total over all on treatment phases (“**Total**”)
- a total over all on treatment phases with BI (“**BI Total**”) (for Part I only)

In Section 15.4 and Appendix 16.2 (Listings) of the CTR displays, the screening and follow-up will additionally be included and no totals will be provided.

For detailed information on the handling of the treatments refer to Technical TSAP ADS (analysis data set) plan and Analysis Data Reviewers guide.

